Any time an adverse event occurs and at least once a year the investigators will conduct a data and safety review. During this review process, the investigators will evaluate any adverse events and determine whether the event changes the risk/benefit ratio of the study and whether modifications to the protocol or consent process are required. When necessary, they will seek recommendations from Vanderbilt University, Wits University and/or Mpumalanga Province research ethics committee.

The VU and South African (Wits and Mpumalanga Province) IRBs will also review the study proposal and annual reports will be submitted as part of the continuing review process. At this time, they will complete the following: (1) reassess the risks and benefits to participants, the informed consent process, and safeguards for human subjects; (2) review participant enrollment and retention; (3) consider any new scientific or therapeutic developments that might impact the safety of participants in the study; and (4) review any adverse events. Changes to the DSMP will be made as needed.

The investigators will adhere to the VU and South African IRBs' policies on unanticipated problems involving risks to participants or others. The following problems would require prompt reporting to the IRBs. This procedure outlines the process for reporting adverse events, serious adverse events, and unanticipated problems involving risk to participants or others.

Investigator Responsibilities

A. The Investigator submits any serious adverse event that requires reporting according to this policy and any other adverse event that may represent an unanticipated problem involving risk to participants or others as follows:

1. A "Report of Unanticipated Problem Involving Risk to Participants or Others" is submitted to the IRB as soon as possible, but no later than 7 calendar days after the Investigator first learns of the event or problem.

This form contains the Investigator's assessment of causality (related or not related to the study) and a description of the actual event;

2. The form also contains an evaluation of whether the event meets the following criteria:

- a. An event that suggests that the research places subjects or others at a greater risk of physical or psychological harm than was previously known or recognized;
- b. Unanticipated (i.e., the event was not foreseeable); and
- c. Related (i.e., likely to have been caused by the research procedures)

3. Finally, any associated materials such as medical record notations or reports with the name and medical record number of the individual redacted (removed) will be included with the report.
4. When applicable, a "Request for Amendment" indicating changes associated with the event or problem is submitted.

Serious Adverse Event (SAE) Reporting

The Division of AIDS Table for Grading the Severity of Adult and Pediatric Adverse Events (DAIDS AE Grading Table), Version 1.0, December, 2004, will be used to determine clinical and laboratory grades of any/all grade 2 or higher events (including signs and symptoms, laboratory abnormalities, and diagnoses).

In addition, any/all deaths, disabilities, malignancies, and/or any other conditions deemed serious and/or debilitating/incapacitating by the clinical team will be reported to all involved ethical review boards. The PI will submit SAE information as required by local regulatory or other local authorities, and the research team will adhere to these stringent requirements and submit full reports detailing any SAEs in a timely fashion (i.e. in accordance with existing standards). After the end of the protocol-defined SAE reporting period stated above, the site will report serious, unexpected, clinical suspected adverse drug reactions if the study site staff becomes aware of the event on a passive basis, i.e., from publicly

Benefits

Traditional healers in this study could potentially benefit from PPE education and skill building and increased engagement with the health system which will likely highlight the importance of protecting themselves from blood exposures. Health care workers in this study could potentially benefit from their additional PPE education and skill building, which could help protect themselves from blood exposure.

9. Limitations

This study will not be powered to assess seroconversion among traditional healers exposed to HIV but will give us proxy outcomes (blood exposure) and implementation outcomes (acceptability, fidelity to PPE use) to predict the success if we developed a larger trial.

10. Dissemination Plan

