1. Traditional healers \geq 18 years of age, who are registered as traditional healers with the government of South Africa, are currently practicing in the Bushbuckridge area, and conduct traditional vaccinations.

2. Biomedical practitioners \geq 18 years of age, who are currently providing health care services to patients at government or private health facilities in Bushbuckridge.

3. Community members \geq 18 years of age, who currently live in Bushbuckridge and sought health care services from a traditional healer in the past year.

Exclusion Criteria

1. Traditional healers <18 years of age, who are not registered as traditional healers with the government of South Africa, are not currently practicing, or do not conduct traditional vaccinations on their patients.
2. Biomedical practitioners < 18 years of age or who are not currently providing health services in the Bushbuckridge area.
3. Community members < 18 years of age or who do not seek health care services from traditional healers.

Calculation of Sample Size & Sampling Strategy

Aim 1: We anticipate recruiting 20 traditional healers and 10 health care workers to achieve data saturation.

Aim 2: With $n=61$ traditional healers per arm, we will have approximately 80% power to detect a difference between intervention arms for the fidelity scores of 0.5 standard deviations, and approximately 90% power to detect a difference of 0.6 standard deviations. These power calculations are based on a two-sample t-test and are likely conservative because the primary analyses will incorporate multiple (correlated) observations per healer. It should be noted that we do not have preliminary data for the fidelity scores; therefore, our power calculations are based on generic standard deviations. Finally, it should be noted that the sample size was primarily based on ensuring adequate power for Aim 3.

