Aims 2 & 3: Traditional healers randomized to both the control and intervention arms will receive PPE education and training, general HIV prevention education and skill building (including condom use, positive prevention, and pre-/post-exposure prophylaxis services), and three educational outreach and coaching visits at the healer's place of practice to provide on-the-ground advice and support for PPE use. These training and educational outreach sessions are designed to allow healers to receive education about bloodborne disease transmission (information), accurately assess their risk of contracting bloodborne illness (motivation), and develop skills to effectively don, doff, and dispose of used PPE (behavior) (Appendices 2 and 3). Outreach visits will focus on delivering five key messages and troubleshoot any issues healers may have in following recommendations. We will assess the impact of our evidence-based PPE intervention on the knowledge, motivation, and behavioral skills developed by traditional healers using the Situated Information Motivation and Behavioral Skills (Situated-IMB) model.⁴⁴ The use of in-class

and educational outreach strategies have yielded improvements in clinical care delivery,⁴⁶⁻⁴⁸ including use of PPE,⁴⁹ among physicians, nurses, and community health workers in low-resource settings. These strategies were selected in consultation with traditional healers in Agincourt who reported never having received training on how to protect themselves from exposures based on the strategies used around the world to train health care providers to avoid infection.^{33,36,49-51} PPE use is feasible and acceptable to most healers and their patients already,²⁷ but they lack the knowledge and/or motivation to use gloves properly and regularly.

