Aim 2: Analysis plan for content: A numeric scale will be used to assess the fidelity of the delivery of *each* topic in the training session. Topics include: (1) Delivered information about the definition of PPE, (2) Provided information about when to use PPE, (3) Provided information about what types of PPE to use in different circumstances, (4) Provided information about the appropriate fit of PPE, (5) Provided do's and don'ts of glove use, (6) Provided information about don PPE, (7) Provided information about how and where to remove PPE, (8) Provided information about how to safely store used PPE, (9) Provided information about hand hygiene, (10) Provided instruction and feedback during PPE practice session. Each of the ten training items will be scored (each with a score of 0-10; 10 represents the greatest fidelity to the training guide, 0 not covering the material at all) for a total of 100 points. The summation of all scores across topics will be used to measure fidelity to content for that training session. Each participant will participate in three training sessions. The mean difference between the two interventions in the total fidelity scores will be estimated using mixed effects linear regression models with 95% confidence intervals (CIs). These models will include random effects for the participant (to account for correlation across multiple sessions) and the trainer (to account for one trainer instructing multiple participants) and a 95% CI will be constructed. The outcome will be transformed as necessary to meet modeling assumptions. Covariates will include patient volume, sex, and baseline age. Any missing data will be imputed using chained equations with 20 imputation replications. Based on prior experience working with healers, we anticipate very low rates of loss to follow-up (LTFU). Healers who are LTFU will be censored at the time of their last recorded data collection, and inverse-probability of censoring weights based on healer characteristics randomization will be used, if necessary, to account for differences between healers who are LTFU and those who remain in the study.

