Analysis plan for coverage: We will calculate the percentage of sessions completed as the actual number of sessions completed for a participant divided by the total number of planned sessions. The percentage of sessions completed between the two intervention arms will be compared using mixed effects Poisson regression with the number of planned sessions (in most cases 3) as an offset. 95% confidence intervals will be constructed. The models will include random effects for the trainers. Covariates will include patient volume, sex, and baseline age. Missing data and LTFU will be handled as described above.

Aim 3: The analysis will follow intent-to-treat protocol. Our primary outcome is the proportion of a healer's procedures that were conducted using latex gloves (numerator = number of procedures with blood exposure, denominator = number of procedures). We will compare the blood exposure proportions between the two study arms using a negative binomial regression model. In the negative binomial regression, the outcome will be the number of times gloves were used and the number of procedures performed by the healer (number of razor blades) will be included as an offset. Such an analysis is appropriate because it properly accounts for heterogeneity between healers in the number of procedures performed, and the resulting estimates from the model can be interpreted as relative proportions (proportion of procedures with blood exposure in Arm 1 vs. proportion of procedures with blood exposure in Arm 2). In addition to our primary intervention

exposure variable, we will include healer sex and baseline age as covariates in our model. Sensitivity analyses will compare blood exposure proportions between the two intervention arms using a two-sample t-test; a Wilcoxon rank sum test will be fit as needed to avoid normality assumptions.

Based on prior experience working with healers, we anticipate very low rates of loss to follow-up (LTFU). Healers who are LTFU will be censored at the time of their last recorded data collection, and inverse-probability of censoring weights based on healer characteristics randomization will be used, if necessary, to account for differences between healers who are LTFU and those who remain in the study. Missing data will be imputed using chained equations and 20 imputation replications.

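### The content-fidelity model has no session term and the handling of undelivered sessions is unstated, so a coverage difference could leak into the content contrast if scores also vary by session

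*Combined protocol and SAP*

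**What the plan says.** Section 7, Data Analysis, Aim 2 (content) gives each training session a total score out of 100, plans three sessions per healer, and compares arms by mixed-effects linear regression. On the model terms it says "These models will include random effects for the participant (to account for correlation across multiple sessions) and the trainer" and "Covariates will include patient volume, sex, and baseline age". Session number and session type are not mentioned. The same paragraph imputes any missing data by chained equations with 20 replications. It censors healers lost to follow-up, with inverse-probability weights if needed, and expects very little loss.

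The next paragraph makes session completion an outcome in its own right, compared between arms: "We will calculate the percentage of sessions completed as the actual number of sessions completed for a participant divided by the total number of planned" (that is, out of all those scheduled).

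Section 5, Measurement of Results, Aim 2 has fidelity rated in both the week-long course and the outreach sessions. Section 5, Study Procedures, Aims 2 & 3 adds: "Outreach visits will focus on delivering five key messages and troubleshoot any issues healers may have in following recommendations". The rating form in Appendix 2 has ten topics, and a topic not discussed scores 0. The course plus three outreach visits makes four contacts, while the analysis refers to three sessions. Which three are scored is not stated.

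**The concern.** Content and coverage are meant to be separate constructs. With no session term, the model treats a healer's scores as exchangeable apart from the healer and trainer effects. A visit built around five messages need not score like a full course on a ten-topic form, so mean scores may well differ by session. If one arm also completes fewer of the later sessions, its average comes from a different mix of sessions, and the arm contrast absorbs part of that difference. The participant random intercept does not remove this. It allows for correlation within a healer, not for which sessions were observed.

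Fidelity is there to help interpret the effect on PPE use, and section 7 plans to explore whether intervention effects differ by trainer fidelity. A content difference that is partly a coverage difference would blur both uses.

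**Working it through.** Inputs from the documents: 61 healers per arm, three planned sessions, one score per session, and the Aim 2 power statement in section 4. That section says "our power calculations are based on generic standard deviations", so no score SD is available.

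Assumed, because the documents are silent: two-sided alpha 0.05 for Aim 2 (stated only for Aim 3); a linear trend of b = 0 to 1 SD per session, in units of the SD of a single session score; within-healer correlation ρ from 0.1 to 0.7; later sessions are the ones missed; and these completion patterns.

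| Coverage | Better-covered arm: 3 / 2 / 1 sessions | Other arm: 3 / 2 / 1 sessions |
|---|---|---|
| 97% vs 90% | 93 / 5 / 2% | 80 / 10 / 10% |
| 100% vs 80% | 100 / 0 / 0% | 60 / 20 / 20% |
| 100% vs 67% | 100 / 0 / 0% | 30 / 40 / 30% |

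For example, (3×0.60 + 2×0.20 + 1×0.20)/3 = 0.80.

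Step 1, the plan's own figure. Section 4 claims "approximately 80% power to detect a difference between intervention arms for the fidelity scores of 0.5 standard deviations". For the larger of its two differences it claims "approximately 90% power to detect a difference of 0.6 standard deviations". Power ≈ Φ(d√(n/2) − 1.96), with √(61/2) = 5.523.
- d = 0.5: Φ(2.761 − 1.96) = Φ(0.801) = 78.9% (exact t: 78.2%).
- d = 0.6: Φ(3.314 − 1.96) = Φ(1.354) = 91.2% (exact t: 90.8%).

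Both agree with the plan to within two points, so 0.5 SD is a fair yardstick.

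Step 2, bias with no session term and undelivered sessions left out. In a random-intercept model a healer with n sessions has weight w(n) = n/(1 + (n−1)ρ). The arm mean is Σ p(n)w(n)m(n) / Σ p(n)w(n), where p(n) is the share of healers with n sessions and m(n) is the mean over the first n sessions: m(1) = 0, m(2) = b/2, m(3) = b.

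Worked case, 100% vs 80%, b = 1, ρ = 0.5: w(3) = 1.5, w(2) = 1.333, w(1) = 1. The fully covered arm has mean 1. The other has (0.6×1.5×1 + 0.2×1.333×0.5 + 0)/(0.9 + 0.267 + 0.2) = 1.033/1.367 = 0.756. The false difference is 0.244 SD.

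False difference in SD over ρ = 0.1 to 0.7:

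| Coverage | b = 0 | b = 0.25 | b = 0.5 | b = 1.0 |
|---|---|---|---|---|
| 97% vs 90% | 0 | 0.014–0.023 | 0.028–0.045 | 0.057–0.091 |
| 100% vs 80% | 0 | 0.046–0.067 | 0.093–0.134 | 0.185–0.268 |
| 100% vs 67% | 0 | 0.093–0.117 | 0.187–0.234 | 0.373–0.467 |

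With the same completion pattern in both arms (93% each) it is zero at every b.

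Step 3, simulation with no true arm effect (800 trials per scenario, ρ = 0.5). Type I error without a session term:

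| Coverage | b = 0.25 | b = 0.5 | b = 1.0 |
|---|---|---|---|
| 97% vs 90% | 4.6% | 4.9% | 6.6% |
| 100% vs 80% | 6.6% | 11.6% | 22.4% |
| 100% vs 67% | 11.1% | 27.4% | 66.0% |

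The simulated biases at b = 1 (0.061, 0.180 and 0.387) fall below the closed-form values at ρ = 0.5 (0.080, 0.244 and 0.442). A likely reason is that the unmodelled trend enters the residual and lowers the fitted correlation. With complete data the within-healer variance becomes 0.5 + 1 = 1.5, the between-healer component (0.5 + 0.5/3) − 1.5/3 = 0.167, and the fitted ρ 0.167/1.667 = 0.10. At ρ = 0.1 the closed form gives 0.057, 0.185 and 0.373.

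Step 4, remedies in the same simulation. Session as a fixed factor: bias at most 0.013 SD, type I error 3.6–6.6%. Session-specific multiple imputation (20 imputations) with no session term: bias at most 0.013 SD, type I error 4.2–5.9%.

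Limits: the trainer random effect was left out, only later sessions were missed, and Monte Carlo error is about 0.8 points near 5%.

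**The case against.** The trend is an assumption. The plan has no preliminary fidelity data, and its sentence on outreach describes those visits collectively, so it is no evidence that visits 1, 2 and 3 differ from one another. If the course is one of the scored contacts, the text suggests one step from course to outreach, not a steady trend. This stands.

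A large coverage gap may be unlikely, since outreach takes place at the healer's own practice and very little loss to follow-up is expected. This stands in part. Loss to follow-up is not coverage: a healer can stay in the study and miss a visit, and the censoring weights do not address that.

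The imputation rule may already solve the problem. If the three scores are held as three variables, chained equations are session-specific and step 4 shows that the bias goes. That is one reading. The plan does not say that an undelivered session is missing data, and the coverage analysis counts it as not completed.

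The covariate list may not be exhaustive, and the sample size was set mainly for Aim 3. Both are fair, and both limit the weight of the point.

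A reader might infer that unequal coverage alone distorts the content contrast, or that the planned analysis is bound to be biased in favour of one arm. The documents support neither. Without a session trend the bias is exactly zero. Rising scores penalise the less-covered arm and falling scores favour it.

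**Conclusion.** The point holds as a conditional gap in specification, not as a demonstrated bias. It needs three things together: mean scores that differ by session, different mixes of completed sessions by arm, and undelivered sessions omitted or imputed without session. The plan makes the first plausible and foresees the second by testing coverage between arms. It leaves the third open.

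Under the assumed values the effect is small for small gaps: at most about 0.09 SD at 97% against 90%, even at 1 SD per session, against a design target of 0.5 SD. It becomes material only with large gaps and strong trends: about 0.19 to 0.27 SD and 22% type I error at 100% against 80% with a 1 SD trend. The larger figures at 100% against 67% show sensitivity only, since nothing in the documents supports a gap and trend of that size.

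These are SDs of a single session score. A three-session healer mean has SD √((1+2ρ)/3), or 0.816 at ρ = 0.5, so 0.244 becomes 0.30 and 0.080 becomes 0.10 on that scale. The conclusion is the same.

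**What to change.** In section 7, Aim 2 (content), add session number as a categorical fixed effect, with course versus outreach distinguished if both are scored. State which contacts are the scored sessions. State whether an undelivered session is treated as missing for the content outcome. If it is imputed, include session in the chained-equations model or impute the session scores as separate variables. Report the session-adjusted arm difference as the content result.

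The cost is a few sentences and about two degrees of freedom. No new data are needed beyond recording which session each score belongs to. If scores turn out not to vary by session, the extra term does no harm.

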Aim 2: We will rate training fidelity via two constructs: (1) content and (2) coverage^{41,42} during the week-long training session and community-based outreach sessions (Appendix 2). Understanding the fidelity of training delivery is essential to interpreting the effect of the intervention on PPE behavior change. If HCW + healer teams can deliver training with greater or equal fidelity than HCWs alone, PPE training can be more quickly scaled up nationwide (given the large number of healers) and conducted at lower cost (healers charge considerably less per hour than HCWs). We believe that the healer + HCW teams may have more motivation to deliver the program with fidelity during community-based sessions than the team of HCWs alone because of healers' desire to protect their peers living in their own community. Three HCWs who volunteer to work on this project will be randomly assigned to the intervention team (along with the healers), with six volunteer HCWs assigned to the control arm.

Aim 3: Healers will complete an interviewer-assisted survey immediately post training (Appendix 3) using the Consolidated Framework for Implementation Research framework⁴³ (compatibility of PPE with current behavior, peer pressure to use PPE, perception of the inclusiveness of the training process, cost) and individual characteristics from the situated-IMB model (Figure 3)^{44,45}. During the six months of the trial, healers in each arm will record data on our primary outcome: the proportion of injections conducted using PPE in two ways.

(1) Collect used sharps and PPE. Healers will be given containers to place all used gloves and razors/sharps to both ensure healer safety and allow us to count materials used (healers use gloves and a single razor once per patient and subsequently throw them into latrines or trash piles). We will use the *number of glove pairs as the numerator* (number of times they used gloves during procedures) and the *number of razor blades as the denominator* (number of injections given). While some may be concerned with social desirability bias, healers have been told for years to use gloves and were very open with us about their non-use. Healers have no reason to

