under- or over-inflate their PPE use as it will not benefit them- in fact, they would have to buy the razor blades or travel to a health facility to obtain additional latex gloves, something that seems unlikely in this population. (2) Self-report. Healers will record behavior (injection and glove use) every time they conduct an injection.

Study Procedures

Aim 1:

Phase 1: Information Gathering: We will interview select traditional healers and health care workers who have received some training on the use and disposal of PPE. Among traditional healers we will probe into how we can improve the training they receive, their preferred method of receiving information, and perceived gaps in their knowledge. From health care workers, we will gather information about how they were trained in the donning and doffing of PPE, aspects of the training that they believe would be most useful to traditional healers, and strategies to deliver these messages in a way that would be accessible to those with low levels of literacy.

Phase 2: Production of Draft Program: After we gather information from healers and health care workers, we will produce a draft of our training program. Our team will ensure we are maintaining fidelity to core elements and the underlying theoretical framework of the original evidence-based intervention. If there are substantive changes, we will draft additional measures to assess impact of these changes on the intervention outcomes. We will also develop quality assurance metrics (e.g. to ensure healers are using and disposing of PPE safely) and process measures to track the program's success.

Phase 3: Topical Experts: With our advisory counselor, as well as local leaders (e.g. leader of the traditional healer association, head of HIV care and treatment in the Department of Health), we will elicit feedback on our draft protocol. These experts will be tasked to focus on "big picture" issues, specifically sustainability and integration into district, provincial, and national level systems.

Data Collection:

In-depth Interview Question Guide: All participants will provide feedback on the acceptability, feasibility, and appropriateness of PPE training via open-ended questions (e.g. What information was most useful?), as well as questions about perceived barriers and facilitators to PPE training (How difficult will it be to use the sharps containers?) (Appendix 1).

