1= traditional healer

2= Religious healer (Muslim)

3= Religious healer (Christian)

4= Herbalist

5= Prophet

8= Other

8a. If other, please specify:

11. Have you ever received an HIV test? Yes No

12. If you are willing to share the results, what were they?

0= Refused to share

1= Negative

2= Positive

3= Don't know/ didn't return for results

4= Indeterminate

13. HIV Rapid Test Results (baseline and end line, only used if negative or no results from prior test, we don't re-test positives)

1= Negative

2= Positive

4= Indeterminate

5= Refused Test

Demographics for health care providers

1. Sex of respondent. 0= Male 1= Female

2. How old are you today (age in years)?

3 What is the highest grade of education that you have completed?

4. What languages do you speak fluently? (check those English that apply)

Shangaan

Afrikaans

Portuguese

Zulu

Xhosa

Other

5. What community do you live in?

6. What is your marital status?

1= Single

2= Married

3= Living with partner

4= Widowed

5= Divorced

6= Separated

7. What is your current clinical position?

8. Health care facility where you are employed?

Main Questions:

1. Can you tell me about any training you have received to use gloves and/or a mask or face shield when you are treating a patient? Who provided this training? What are the skills you have learned?

2. Can you tell me if you use gloves during each procedure where you could be exposed to blood? If you don't use gloves, do you use something else, like a plastic bag?
3. If you do not always use gloves, can you tell us why? Probe: cost, access, don't believe in germ theory of disease, God will save me) Are there specific patients where you ensure that you always wear gloves? (e.g., someone you suspect has HIV?)
4. Now that COVID is widespread, do you use a mask when you have patients in your hospital or home? If you don't use a mask, can you tell me why not? Are there specific patients where you always use a mask? (e.g., someone you suspect has COVID-19 or TB?). If you use a mask, what type of mask do you use (e.g. cloth, surgical [the blue looking ones], N95)? Where did you get the mask? If you had to pay for the mask, how much did you pay?

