5. How has COVID affected your physical interaction with patients? Do you see patients in person (more or less than before)? Do you talk to patients over the phone (more or less than before)? If you see patients in person have you changed the way that you do anything (length of consultant, change in traditional vaccinations or other procedures?)
6. What effect has COVID had on you as a traditional healer?
5. Have you ever had a patient ask you about your gloves/mask use? If so, did this happen during the current COVID situation? What did the patient ask and what was your response?
5. We want to provide training to you and your colleagues to ensure traditional healers are protected from infectious diseases. Would you prefer to learn these lessons from another traditional healer or from a health care provider? Why? What do you think are the most important lessons for you to learn?
6. Lets talk about disposal of gloves for a moment. When you decide that you need to protect your hands, do you put gloves/bags on both hands or only one? Do you reuse them or dispose of them? If you reuse them, how do you clean them? If you dispose of them, where do you put them?
7. Lets talk about disposal of masks for a moment. What kind of masks are you using, one that can be washed or one that needs to be disposed of? If you use one that can be washed, how often do you wash it? If you use a disposable one, where are you getting them? How long do you use it before putting it in the trash?
8. We will be providing sharps containers and containers for used gloves/bags and razor blades for those healers who enroll in the study. We will come by every week to collect these materials. Do you think anyone would have difficulty using it?
9. Our aim in providing this training and material is to ensure traditional healers are protected from infectious disease. Besides the training, masks, gloves and sharps containers. As a traditional healer, is there anything else that you think we should be discussing or considering? If so, what?
9. Is there anything else about glove or mask use that you think we should know about?

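### The Aim 3 model estimates a ratio of glove-use proportions, but the plan reads it as a ratio of blood-exposure proportions, and non-glove barriers are not recorded separately

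*Combined protocol and SAP*

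**What the plan says.** **Measurement of the outcome.** Section 5 (Measurement of Results, Aim 3) says healers will record "the proportion of injections conducted using PPE in two ways". The first way is a count of collected materials: "Healers will be given containers to place all used gloves and razors/sharps", with the "number of glove pairs as the numerator" and razor blades as the denominator. The second is self-report: "Healers will record behavior (injection and glove use) every time they conduct an injection".

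**Analysis of the outcome.** Section 7 (Data Analysis, Aim 3) calls the outcome the proportion of a healer's "procedures that were conducted using latex gloves". The parenthesis that follows gives the numerator as procedures with blood exposure. The model is then a negative binomial regression of the number of times gloves were used, with razor blades as the offset. Its estimate is to be read as the proportion of procedures with blood exposure in one arm relative to the other. Blood exposure is not defined.

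**Other barriers.** Study Procedures (Aims 2 & 3) describes the healers to be influenced as those who use no barrier of any kind against blood. The healer interview guide in Appendix 1 asks: "If you don't use gloves, do you use something else, like a plastic bag". Item 8 of that guide says: "We will be providing sharps containers and containers for used gloves/bags and razor blades for those healers who enroll in the study". Section 5 mentions no bags.

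**The concern.** There are two separate problems.

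The first is direction. A model with glove counts as the response cannot give a ratio of exposure proportions. If the stated interpretation is applied literally, a successful intervention, with a ratio above 1, would be reported as more blood exposure.

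The second is meaning. Even after the direction is corrected, treating every ungloved procedure as an exposure assumes that no other barrier is used. The protocol's own text makes that uncertain. A healer who moves from bags to gloves raises the glove count but does not change how often some barrier was present. As described, the records would not separate a bagged injection from a bare-handed one, so the question could not be answered afterwards.

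This matters because exposure is the stated target. Aim 3 is framed as healer exposure to patient blood, the text introducing Table 1 describes its differences as differences in blood exposure, and Section 9 treats blood exposure as the proxy outcome for a larger trial.

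**Working it through.** **1. The plan's own figure.** Inputs from the Aim 3 sample size text: 61 healers per arm, SD 0.39, difference 0.20 in glove use, alpha 0.05. The test is a two-sample t-test with 120 degrees of freedom, taken as two-sided because that reproduces the table. The noncentrality is 0.20 / (0.39 × √(2/61)) = 2.83. Power is 80.22%, and 61 is the smallest n per arm that reaches 80%. All nine rows of Table 1 reproduce to two decimals. The sample size is sound for glove use.

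**2. Which quantity is counted.** Set side by side:
- Section 5, materials: glove pairs over razor blades.
- Section 5, self-report: injections and glove use.
- Sample size: proportion of glove use.
- Section 7, model: times gloves were used, offset by razor blades.
- Section 7, parenthesis and interpretation: procedures with blood exposure.

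The first four agree. Only the last differs.

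**3. Direction.** Take glove use as 0.40 in the control arm and 0.60 in the intervention arm (assumed levels; the 0.20 difference is the plan's).
- Ratio of glove-use proportions: 0.60 / 0.40 = 1.50.
- Ratio of ungloved proportions: (1 − 0.60) / (1 − 0.40) = 0.40 / 0.60 = 0.67.

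The second is not the reciprocal of the first by rule. It depends on the levels. With glove use of 0.20 vs 0.40, the glove ratio is 2.00 and the ungloved ratio is 0.60 / 0.80 = 0.75. One cannot be relabelled as the other.

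**4. Non-glove barriers.** The documents give no frequency of bag use, so the following is an assumed range. Let g be the glove proportion and b the share of ungloved injections done with a bag. Then:
- any barrier = g + (1 − g)b
- no barrier = (1 − g)(1 − b)

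Power uses the plan's t-test with SD 0.39 assumed to carry over from glove use.

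| b control, b intervention | Any barrier, control vs intervention | Difference | Power | No-barrier ratio |
|---|---|---|---|---|
| 0, 0 | 0.40 vs 0.60 | 0.20 | 80.2% | 0.40/0.60 = 0.67 |
| 0.1, 0.1 | 0.46 vs 0.64 | 0.18 | 71.5% | 0.36/0.54 = 0.67 |
| 0.2, 0.2 | 0.52 vs 0.68 | 0.16 | 61.3% | 0.32/0.48 = 0.67 |
| 0.3, 0.3 | 0.58 vs 0.72 | 0.14 | 50.3% | 0.28/0.42 = 0.67 |
| 0.2, 0.1 | 0.52 vs 0.64 | 0.12 | 39.2% | 0.36/0.48 = 0.75 |
| 0.1, 0.2 | 0.46 vs 0.68 | 0.22 | 87.1% | 0.32/0.54 = 0.59 |

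With the same b in both arms the difference is 0.20 × (1 − b), whatever the glove levels, and the no-barrier ratio does not move. With unequal b, both the difference and the ratio can move in either direction.

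**The case against.** The best defence is that the operational plan is consistent. Wherever something is counted or modelled, it is glove use, and the Aim 3 hypothesis is about glove use too. PPE in Section 5 is a label; the numerator stated there is glove pairs. That stands.

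A reader might infer that the plan holds two opposing rules, one counting a bagged injection as protected and the other as exposed. The documents do not support this. No text counts a bag as protected, and the definition of PPE in the background does not name bags.

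A reader might also infer that bags will certainly be in the containers. Bags as container contents appear only in an Aim 1 interview question, which also speaks of weekly collection where Study Procedures has monthly. The guide is therefore weak evidence of trial procedure, and asking about bags does not show that they are used. Bags may be in the containers; no more can be said.

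Nor is there good ground for saying that non-latex gloves would be rejected. Section 7 uses latex once as a descriptor and then models gloves without qualification.

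What the defence does not answer is the exposure interpretation in Section 7, which is wrong as written even if no healer ever uses a bag.

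**Conclusion.** The point holds in two parts. The exposure numerator and interpretation in Section 7 contradict the modelled count and must be corrected; this rests on no assumption. In addition, an ungloved procedure cannot be equated with an exposure while other barriers are anticipated but not separately recorded.

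The size of the second part is unknown. Under the assumed levels, bag use in the same 10% to 30% of ungloved injections in both arms gives an any-barrier difference of 0.18 to 0.14 (power 71.5% to 50.3%). The unequal cases shown give 0.12 (39.2%) or 0.22 (87.1%), and no bag use changes nothing.

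It would be tempting to read these figures as a loss of power for the trial. They are not: they apply only to an any-barrier comparison, and the primary glove-use comparison keeps its 80.2%.

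**What to change.** - In Sections 5 and 7, define the primary outcome once: pairs of disposable gloves of any material over razor blades.
- Delete the parenthesis in Section 7 that makes blood exposure the numerator, and state that the estimate is a ratio of glove-use proportions.
- Define blood exposure for analysis purposes. Base any statement about it on a sensitivity analysis of procedures with neither a glove nor another barrier.
- Align the container descriptions in Section 5 and Appendix 1.
- Tally bags and other improvised barriers separately at the monthly collection, and add them to the healer's form. The form is completed at each injection, so it can show directly which procedures had no barrier; the container tally is a check.

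These are changes to measurement and analysis. They do not say which barrier healers should use. The cost is one extra tally at a visit already planned, one more entry on the form and one sensitivity analysis. The drawback is that the glove-use and no-barrier results may differ, and both would have to be reported.
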